8.6 Data Safety Monitoring Board

The Node Quality Assurance Coordinator will perform on site review of 100% of the informed consent forms, inclusion/exclusion criteria, randomization assignments, and serious adverse events.

Study Procedures

The initial quality assurance monitoring visit should, whenever possible, take place no later than two weeks after the 3rd participant is enrolled at a CTP. A full on site review of 100% of the following should occur for the first ten participants.

- Review all procedures and forms for screening, informed consent forms, baseline assessments and randomization.
- Review all procedures and documentation of urine drug screens.
- Review adverse events.
- Review all other case report forms.

The Node Quality Assurance Coordinator will randomly review 10% of the remaining participants. Moreover, to monitor the quality of data for our primary outcome measure at least 50% of the remaining timeline follow back data will be randomly reviewed throughout the course of the study. This creates an expectation for all professional staff that more than 1 out of every 2 assessments will be thoroughly reviewed encouraging a context where research assistants are highly motivated to do thorough assessments of drug use.

Quality Control of BSFT Administration

The clinical forms and procedures will also be monitored by the Node Quality Assurance Coordinator. The Coordinator will review the query reports from the Lead Node for accuracy and timeliness. The first 10 queries for each BSFT therapist will be reviewed and 25% of the remaining queries for each BSFT therapist will be reviewed.

In addition, the Node PI and NIDA monitors will perform schedule reviews as deemed necessary.

Depending on how data are collected at each site, either the Node Quality Assurance Coordinator will examine data forms on site or it will be done at Node's Data Management Center. Missing, incomplete, or out of range data will be identified. The CTP PI and Research Assistant will be notified as soon as possible about potential errors. The Node Quality Assurance Coordinator and Node Data Management Center will verify that corrections have been made.

9.0 VARIATIONS IN PROTOCOL IMPLEMENTATION

Based on the characteristics of adolescents at CTPs it may be necessary to expand inclusion criteria to ensure an adequate sample for the current study. This should be limited however to avoid creating variability in the sample across CTPs. One area that will not threaten the ability to interpret cross-site findings is the radius where adolescents and family members reside which will be established by each CTP separately.

10.0 STATISTICAL ANALYSIS

10.1 Objectives of Analysis

The primary goal of this study is to examine the effectiveness of BSFT with adolescent drug-abusers. Specifically, it is hypothesized that:

Hypothesis 1: BSFT will be significantly more effective than TAU in reducing adolescent drug use, defined as the percentage of drug use days in 28-day periods.

Secondary hypotheses examine the relative effectiveness of BSFT over TAU in:

Hypothesis 2a: Engaging adolescents and family members in treatment

Hypothesis 2b: Decreasing adolescent delinquent behaviors and conduct problems

Hypothesis 2c: Decreasing adolescent sexually risky behaviors

Hypothesis 2d: Increasing adolescent prosocial activities (e.g., school, employment)

Hypothesis 2e: Improving family functioning (e.g., parenting, parent-adolescent relations).

10.1.1 Overview of Analysis

Testing of Distributional Assumptions. Statistical tests for univariate and multivariate normality (tests of skew & kurtosis) as well as visual inspections of the empirical distributions will be conducted. For all hypotheses residuals from the statistical analysis will be examined to determine that distributional assumptions are met. If these analyses show significant deviations non-parametric, or non-normal based versions of the proposed hypothesis tests will be devised. For example, for count data of small range, Poisson regression is indicated (Koch, Atkinson & Stokes, 1986).

Sampling and Generalizability. To establish comparability for subsequent analyses, comparisons of demographic characteristics between the following groups of participants will be conducted: participants who agree to participate (sign consent), and participants who are randomized. Analyses will also document the reasons for non-eligibility and reasons for non-participation of those eligible. Further comparisons will be made to the groups that remain in the study through various assessment times as described below in Missing Data and Attrition.

Urn Randomization. Randomization will be conducted separately by the CTP using a telephone call-in procedure developed by the Veteran's Affairs. This procedure uses an urn randomization program to increase the likelihood that treatment groups are balanced on two characteristics: Ethnicity/ race (Hispanic, African-American, other) and Level of Drug Use (any drug diagnosis other than alcohol or tobacco, no drug diagnosis) at baseline. This will ensure balance across the two treatment conditions.

All variables included as factors in the urn program will be included as covariates in the primary test of the intervention effectiveness. In addition, age, gender, baseline levels of psychiatric co-morbidity status (no comorbidity, externalizing disorder/s, internalizing disorder/s, internalizing and externalizing disorders), primary drug of abuse, family type and family-peer functioning will be controlled due to their anticipated relationship to most of the outcomes.

Missing Data and Attrition. Analyses will be conducted to identify patterns of attrition and to determine if there is differential attrition by treatment condition. Attrition between conditions will be captured with the use of contact logs, and termination forms. To minimize any impact of attrition on the test of hypotheses, intent-to-treat analyses will be conducted for all hypotheses. Note that individuals that are placed in more restrictive settings for brief periods of time may continue to be included in subsequent assessments. Data will be collected for these individuals at all scheduled timepoints (if possible). The primary outcome measure will be used to identify days that the adolescent was placed in a restrictive environment.

Missing items from multi-item scales will be imputed using the Expectations Maximization (EM) algorithm (Little & Rubin, 1987); however, missing outcome measures (e.g. caused by missing an assessment) will not be imputed. Rather, the hypotheses will be modeled in an intent-to-treat fashion with a maximum likelihood algorithm, which allows the inclusion of cases with missing data (this is possible with the assumption that data are missing

at random). Note that the protocol calls for continued assessment of cases that drop out of intervention in the hope of minimizing all forms of missing data.

Reliability. When appropriate, reliability of all measures and outcomes will be assessed using confirmatory factor analysis. To confirm internal consistency reliability, estimates of Cronbach's alpha for each of the outcome variables (e.g., drug use, externalizing problem behaviors, family functioning) will be determined with a confirmatory factor analysis (Fornell & Larcker, 1981). The indicators of the outcomes in this protocol are scales of established reliability and validity. For any indicator/scale with an alpha < .70 (in this sample), items with low item-total correlations will be trimmed from the scale and the scale re-assessed for reliability. In the confirmatory factor analyses of the outcome variables based on these indicator/scales, should the overall fit of these models prove inadequate (Comparative Fit Index < .95 or standardized root mean squared residual > .06 (Hu & Bentler, 1999; Kline, 1998), additional modifications of the measurement model will be made to achieve an adequate fit. Specifics of the measurement models are described below under "Outcomes and Hypotheses".

Baseline and Other Planned Interim Analyses. The logistical plans for this protocol include the introduction of sites in waves, thus we plan to examine baseline data in waves. Once baseline data has been collected from a particular site, a "soft-lock" of the data from that site will be performed in accordance with the Data Management and Analysis Committee's SOP on Baseline Analyses. Once all necessary quality control is done on this data a series of analyses will be done to examine the issues described above: distributional assumptions, sampling and generalizability, balance of the randomization, and reliability of the proposed measurement scales within this site. Once data from all sites in the study have been 'locked,' similarities across sites will be described and differences across sites on the baseline assessment measures will be tested. In addition, confirmatory factor analysis of all constructs (described below in the hypotheses) will be performed. Once each follow-up time point is completed at each site, a similar procedure will be done each of the follow-up time points. Note that all of the follow-up descriptive analyses will be done blind to condition and that these analyses will not require a penalty for interim efficacy analyses, because efficacy of the intervention will not be examined.

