7.7.7 Family Functioning (Hypothesis 2e)

Hypothesis 2e: BSFT will be significantly more effective than TAU in improving family functioning.

- Parenting Practices Questionnaire of The Chicago Youth Development Study. *Parenting practices* will be measured through 47 questions on parent and adolescent reports (Gorman-Smith, Tolan, Zelli, & Huesmann, 1996). The Parenting Practices Measure, was derived from the parental supervision and discipline interview used in the Oregon Youth Study and Pittsburg Youth Study (Thornberry, Huizinga, & Loeber, 1995). Factor analyses have identified four factors 1) Positive Parenting, 2) Discipline Effectiveness, 3) Avoidance of Discipline, and 4) Monitoring. Positive parenting refers to the use of positive rewards and encouragement of appropriate behavior. Discipline effectiveness is a measure of how effective parental discipline is in controlling the youth's behavior. Avoidance of discipline refers to the parent's avoidance of providing consequences or disciplining for fear of the youth's behavior escalating. Monitoring is a measure of monitoring and involvement in daily activity and routines and knowledge of youth's whereabouts throughout the day. Reports of discipline effectiveness and avoidance of discipline are gathered from parents only. Estimates of positive parenting and extent of monitoring are gathered from both parent and child. Internal consistency reliabilities of each of the subscales ranged from .68 to .81. Confirmatory factor analyses have consistently identified two latent constructs of Discipline and Monitoring which will be the two indicators of parenting used in the family functioning composite (Gorman-Smith et al., 1996). All four factors in this inventory will be used as indicators of parenting practices.
- Family Environmental Scale. The Family Environmental Scale (FES; Moos & Moos, 1986) is a widely used measure that was developed to measure social and

environmental characteristics of families. This measure has been used in thousands of studies to capture critical aspects of family functioning. In this study, we will be using the cohesion and conflict subscales of the FES, administered to both parents and adolescents. Internal consistency reliability estimates for the subscales range from 0.61 to 0.78. Conflict and cohesiveness subscales will be administered to measure family functioning.

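### Item trimming, model modification and estimated loadings are not fixed across time points, so the Hypothesis 2b–2e composites can change in content or scale within one growth model

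*Protocol*

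**What the plan says.** Protocol section 10.1.1 (Reliability) sets a mandatory rule. For any scale whose alpha in the sample is below .70, "items with low item-total correlations will be trimmed from the scale and the scale re-assessed for reliability". If the confirmatory factor model misses its fit limits (CFI below .95 or SRMR above .06), "additional modifications of the measurement model will be made to achieve an adequate fit".

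Section 10.1.1 (Baseline and Other Planned Interim Analyses) gives the timing. As each site's baseline is soft-locked, one of the things examined is "reliability of the proposed measurement scales within this site". After all sites are locked, "In addition, confirmatory factor analysis of all constructs (described below in the hypotheses) will be performed". Then: "Once each follow-up time point is completed at each site, a similar procedure will be done each of the follow-up time points". The same paragraph adds that "all of the follow-up descriptive analyses will be done blind to condition".

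Section 10.3 (Hypothesis 2b) uses equal weights if reliability is sufficient and otherwise factor scores from the fitted loadings. Hypotheses 2c, 2d and 2e reuse that construction. The composites are analysed as in Hypothesis 1. Under sections 10.2.1 and 10.2.4 that is a growth curve over the post-baseline times, with the baseline value as covariate and the BSFT-by-time coefficient among the terms tested.

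Section 7.7.7 says of the Parenting Practices instrument, which supplies the 2e composite: "Internal consistency reliabilities of each of the subscales ranged from .68 to .81".

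**The concern.** A growth model needs one metric. If an item is dropped at T8 but kept at T4, the two scores are different quantities, and part of the change between them comes from the scoring. If loadings are re-estimated at each wave, the weights and possibly the scaling move as well. The baseline covariate then no longer measures the same thing as the outcome it adjusts.

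The protocol fixes the trigger, the trimming, the modification rule and the repetition. It has no sentence holding the result constant over time and asks for no check of longitudinal measurement invariance. At stake is the interpretation of the time trend and the slope contrast in four of the five secondary hypotheses.

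**Working it through.** **Step 1: does any passage fix the scoring?** The relevant places, side by side:

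| Step | Where | Data named | Repeated at follow-up? | Items or weights held fixed? |
|---|---|---|---|---|
| Trim if alpha < .70 | 10.1.1, Reliability | the sample, no wave named | reliability check repeated | no |
| Modify model to fit | 10.1.1, Reliability | none named | factor analysis repeated | no |
| Equal weights or estimated loadings | 10.3, Hypothesis 2b | none named | not stated | no |

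The repeated factor analysis covers the constructs of the hypotheses, and section 10.3 bases the choice of scoring on that analysis. Following the text can therefore give wave-specific items or loadings, although it does not say that scores must be rebuilt at each wave.

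**Step 2: how easily could the trigger differ between waves?** The protocol gives no figure to reproduce, so this is an illustration. Inputs: trigger .70 (10.1.1); N = 480 (10.4); reported reliabilities .68 to .81 (7.7.7). Assumptions: 5 to 15 items per scale, the same true alpha at every wave, and four independent waves. By Feldt's result, (1 − α)/(1 − α̂) follows F(n − 1, (n − 1)(k − 1)), so p = P(α̂ < .70) = P(F < (1 − α)/.30). The chance that the rule fires at some but not all of four waves is 1 − p⁴ − (1 − p)⁴.

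For α = .68, k = 9, n = 480: (1 − .68)/.30 = 1.067 and p = .833, so 1 − .833⁴ − .167⁴ = 1 − .4815 − .0008 ≈ .52.

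| True alpha | p, n = 480, k = 5 to 15 | Mixed over four waves |
|---|---|---|
| .68 | 82–84% | 50–55% |
| .75 | under 1% | 2–3% |
| .81 | about 0 | about 0 |

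Allowing for the 28% attrition assumed in 10.4.1 (N = 480, 436, 390, 345; intermediate values assumed; k = 12) gives 55%, 87.5%, 55% and about 3% for true alpha .68, .70, .72 and .75. Positive correlation between waves would lower these figures.

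**Step 3: what does a changed item set do to the slope contrast?** Take an assumed four-item mean score with a constant effect of −0.3 on three items and none on the fourth. Keep all four items at T4 and drop the fourth at T8 and T12. The observed effects are −0.3 × 3/4 = −0.225, then −0.3 and −0.3. With time 0, 4 and 8 months, the least-squares slope is [(−4)(−0.225) + (4)(−0.3)]/32 = −0.3/32 = −0.0094 per month, when the true value is 0. If the treatment affects no item, the effects are 0, 0, 0 and the slope is 0.

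**Step 4: Hypothesis 2b.** Section 10.3 names four indicators, two of them from the DISC Predictive Scales. Table 1 schedules those scales at B1 and T12 only. The 2b composite therefore cannot have the same content at T4 and T8 as at T12, whatever the trimming rule does.

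**The case against.** A reader might infer that trimming, model modification and factor scoring are done separately at each site. The text does not support this. Only scale reliability is examined within site, the factor analysis follows the lock of all sites, and scoring is described once with no site named.

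A reader might also infer that the procedure biases the comparison of arms. It does not under the null: the follow-up runs are blind to condition and both arms are scored alike at a given wave. Blinding does not, however, keep the metric constant.

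The strongest defence is that the follow-up runs are called descriptive, that the scoring text reads in the singular, and that the choice of wave supplying the loadings is a detail for an analysis plan. This has some force: the protocol leaves the matter open and does not order re-scoring. But the trimming rule is mandatory and tied to no wave, and the factor analysis that decides scoring is among the steps repeated. The protocol sets the data-driven rule itself, without the sentence that makes it safe in a longitudinal model.

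The limits on the calculation stand. It counts alpha crossing .70, not items actually removed, and trimming also requires items with low item-total correlations. The .68 to .81 range belongs to one instrument and is no evidence about 2b, 2c or 2d.

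**Conclusion.** The point holds as a gap in a stated rule. The H2b to H2e composites can differ in items or scaling by wave, because the protocol repeats the checks that drive scoring and never fixes their result. The consequence is possible distortion of time trends and, where a treatment effect exists and differs between items or the scaling shifts, of the slope contrast.

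For trimming, the risk is concentrated in scales with true alpha close to .70 and is small by .75 in the pooled sample. These probabilities assume independent waves, 5 to 15 items and trimming decided wave by wave. Any composite scored with estimated loadings is exposed whatever its alpha. The size of the distortion cannot be derived from the protocol; the slope in Step 3 shows the mechanism only. The primary outcome (percentage of drug use days) and engagement (attendance) are not multi-item composites and are untouched.

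**What to change.** State in section 10.1.1: item trimming, model modification and loadings are decided once, blind to condition, on baseline data pooled over all sites; the same items, weights and baseline scaling are applied at every site and at T4, T8 and T12; site- and wave-level reliability and fit are reported and do not change the score.

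For Hypothesis 2b, build the longitudinal composite from the indicators scheduled at all four time points (National Youth Survey Total Delinquency and Youth Self Report Externalizing) and analyse the DISC Predictive Scales separately at T12. Otherwise reconcile section 10.3 with Table 1.

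The cost is wording: the pooled baseline factor analysis is already planned and no new data are needed. The downsides are that a scale whose alpha falls slightly below .70 at a later wave is kept, and that the longitudinal 2b composite rests on two self-report indicators instead of four.

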10.2 Primary Outcome and Hypothesis

Hypothesis 1. BSFT will be significantly more effective than TAU in reducing adolescent drug abuse, defined as the percentage of drug use days in 28-day periods.

Outcome Variable. The outcome variable for this hypothesis is the percentage of days of drug use within a 28-day period. This variable will be constructed from the Timeline-Follow-back instrument and will be measured as the sum of the number of days with positive use in 28-day increments (there are thirteen 28-day periods in this design, B1 and T1-T12). Periods in which the participant is in a restricted environment will be flagged in the database, but will be included in the primary analysis. If there is missing information on the time-line follow-back within a 28-day period, the percentage will be calculated as the percentage of available days in that period, as long as not more than 14 days are missing. There is a chance that data collected at the same assessment point are more related than data collected across assessment points. Our data analysis strategy exploits the nested structure of our data. Thus, in this protocol, 28-day measures of drug use are nested within 13 assessment points, these assessment points are nested within individuals, individuals are nested within community treatment providers. The statistical model, as defined below, accommodates these different nesting factors. From our experience, in models with many levels of nesting, it is not uncommon for some of the random effects associated with these levels to have close to zero variance. Thus, our strategy will be to first examine the trajectories (blind to the condition assignment), and to

estimate the random effects associated with each level of nesting. If any of these are statistically not significantly different from zero, we will drop these from the specification, prior to testing of the hypotheses. Note further, that as described below, the Hierarchical Linear Model (HLM) to be used to test our hypotheses is described with only a linear term in time. During our examination of the levels of nesting we will also examine the trajectories (again blind to condition) to ascertain any higher order polynomial trends in the data. For example, if a quadratic term in time is found to have significant variance over individuals, we will include the quadratic term in the HLM. The model as presented below does not show the nesting of 28-day periods within assessments and only shows the linear term of the growth model in an effort to keep the notational clutter to a minimum.

Analysis. Hypothesis 1 will be tested using hierarchical linear models (HLM) (Bryk & Raudenbush, 1992) to estimate the growth curve of drug use post-randomization. The trajectory of change in drug use will be compared between BSFT and TAU. HLM controls for the nesting of both repeated observations within the same adolescent over time and the nesting of adolescents within a CTP and further allows for a single test of the effect of the intervention across multiple times and sites (see planned post-hoc tests, below). HLM allows for the flexible inclusion of adolescents who may have missed assessments, and allows for non-linearity of the trajectory of change in the dependent measure. Finally, HLM allows us to consider treatment site as a random effect and to examine variability in treatment effects across sites. The treatment of site as a random effect is in keeping with the mission of the CTN to test the general applicability of proven treatments in real world settings. Thus, it is a goal of this protocol to show that BSFT will be efficacious in the population of community treatment providers, not just the community treatment providers in the sample (which a fixed effect specification would imply). This specification of the test actually compares the effectiveness of BSFT relative to the average effectiveness of TAU in the sites in the protocol. The analysis will include as a covariate referral from an institution for the treatment of drug.

HLM conceptualizes the growth curve as separate equations for the intercept and another equation or other equations (if more than linear change is examined) for the slope, though both (all) are estimated jointly. With the addition of treatment site as a random effect, this model is a three level HLM model. These three levels are associated with 1) time, 2) individual and 3) site. There is an additional level, or random effect associated with the nesting of 28-day periods within an assessment. As noted above, prior to testing hypotheses, in an analysis blind to condition, we will fit these 4 different levels (and additional polynomial terms). If any of the random components, or polynomial terms are not significantly different from zero, we will drop them from the model. Note that in the presentation that follows, we just present the substantive levels of the individual and omit the higher order polynomial terms to focus the exposition on the substantive issues (the growth curve and site variation). To facilitate interpretation of the growth curve, time will be centered on the 4-month post-randomization assessment (T4). Thus, the intercept term represents the difference between the two conditions immediately post intervention. If the expected ordinal nature of the outcome measure results in sufficient deviation from normality a Poisson link function will be used.

10.2.1 Level 1

For Hypothesis 1, the time path of percentage of days having used drugs in 28-day periods will be estimated and the growth trajectory will be parameterized to be a function of BSFT intervention status. Additional predictors will be the stratification variables specified in the urn randomization and the other variables, described under the heading randomization (see section 10.1.1) and any baseline variables found to predict the occurrence of missing data. The growth curve analysis will include the times after baseline only, and baseline value of the dependent measure will be included as a covariate (i.e. an analysis of covariance parameterization). The presentation below does not include the baseline value of drug use or

these other additional covariates, to ease the exposition. As mentioned this is a three-level HLM model. Level 1 describes the trajectory over time for an individual participant:

Level 1

$$y_{ijt} = \pi_{ij0} + \pi_{ij1} \cdot a_{ijt} + \varepsilon_{ijt},$$

where y_{ijt} , a_{ijt} , and ε_{ijt} , are % of drug use days, time, and a random (or error) term, respectively, for person i , in CTP j , at observation occasion t . The variable a_{ijt} will be measured as time from assessment point (T4), which occurs four months post randomization. The variables π_{ij0} and π_{ij1} are the intercept and slope of drug use, respectively for person i , in CTP j .

10.2.2 Level 2

The Level 2 model describes the individual intercept, π_{ij0} , and the individual slope term, π_{ij1} as a function of *BSFT*:

Level 2

$$\pi_{ij0} = \beta_{0j0} + \beta_{1j0}BSFT + r_{ij0},$$

$$\pi_{ij1} = \beta_{0j1} + \beta_{1j1}BSFT + r_{ij1}.$$

The *BSFT* variable is a 0-1 or dummy-coded variable that is coded 1 if the participant is receiving BSFT, and 0 otherwise. Given this coding of the *BSFT* variables, β_{0j0} and β_{0j1} are the intercept and slope, respectively, for participants who are in the TAU condition. The parameters, β_{1j0} and β_{1j1} , are the increments to the intercept and slope of the TAU participants, (β_{0j0} and β_{0j1} , respectively), for participants receiving *BSFT* at treatment site j (i.e. intercept for *BSFT*= $\beta_{0j0} + \beta_{1j0}$ and slope for *BSFT*= $\beta_{0j1} + \beta_{1j1}$). Finally, r_{ij0} and r_{ij1} are person-specific random terms for the intercept and slope.

10.2.3 Level 3

The Level 3 model incorporates the variability across treatment sites into the coefficients of the Level 2 model.

Level 3

$$\beta_{0j0} = \gamma_{000} + u_{0j0},$$

$$\beta_{1j0} = \gamma_{100} + u_{1j0},$$

$$\beta_{0j1} = \gamma_{001} + u_{0j1},$$

$$\beta_{1j1} = \gamma_{101} + u_{1j1},$$

At level 3, the u terms are site-specific error terms. In the absence of covariates, γ_{000} is the grand mean of TAU at T4 (immediately post intervention) and $\gamma_{000} + \gamma_{100}$ is the mean of BSFT at T4 and γ_{100} is the treatment effect of BSFT at T4. Again, in the absence of covariates, γ_{001} is the rate of change from T4 to T12 for TAU and $\gamma_{001} + \gamma_{101}$ is the rate of change of BSFT from T4 to T12 and γ_{101} is the treatment effect of BSFT at T4.

Whereas the model to be tested is conceptualized in 3 distinct levels, it is actually estimated as one single equation with multiple fixed and random effects. Substituting in the various equations gives:

$$y_{ijt} = [(\gamma_{000} + u_{0j0}) + (\gamma_{100} + u_{1j0})BSFT + r_{ij0}] + [(\gamma_{001} + u_{0j1}) + (\gamma_{101} + u_{1j1})BSFT + r_{ij1}] \cdot a_{ijt} + \varepsilon_{ijt}$$

or,

$$y_{ijt} = [(\gamma_{000} + \gamma_{100}BSFT) + (\gamma_{001}a_{ijt} + \gamma_{101}BSFT * a_{ijt}) + (\varepsilon_{ijt} + u_{0j0} + u_{1j0} * BSFT + u_{0j1} * a_{ijt} + u_{1j1} * BSFT * a_{ijt} + r_{ij0} + r_{ij1} * a_{ijt})]$$

This model will be estimated using either SAS Proc Mixed (or Proc NLMixed if a non-linear link function is necessary).

